Official title: Microfragmented Adipose Tissue Versus Platelet-rich Plasma for Knee Osteoarthritis: a Randomized Comparative Trial

NCT number: NCT04351087

Document date: March 30, 2023

Platelet-rich plasma versus Adipose-derived stem cell for knee osteoarthritis: A randomized, comparative trial

Principle Investigator (s): [name] MBA & [name]

Co-Investigators:

[name]

[name].

[name]

[name]

[name] MPH

Background

Knee osteoarthritis is a leading cause of disability worldwide.^{1,2} Standard of care treatments for knee OA include activity modification, weight loss, therapeutic exercise and injections like corticosteroids and viscosupplement. These commonly used non-operative treatments focus on symptom palliation, but are not disease modifying.³

Orthobiologics have emerged as a promising treatment for knee OA. The most widely studied orthobiologic is platelet-rich plasma (PRP).⁴ PRP is a dense concentration of platelets derived from autologous whole blood and platelets are concentrated 2-5x compared to baseline.⁵ The platelets have demonstrated anti-inflammatory and chondroprotective properties.⁶ PRP has been shown superior to placebo and viscosupplement for knee OA in several clinical trials.⁷⁻¹⁰

While PRP is the most widely studied and used orthobiologic, it contains only platelets, but no mesenchymal stem cells. Therefore, a simple, office-based intervention able to collect stem cells to treat knee OA would be ideal. Adipose (fat) is a known source of mesenchymal stem cells and it can be easily and safely aspirated in the clinic.¹¹ The adipose tissue aspiration and processing is accomplished through a simple process. After local anesthesia to the site of adipose aspiration (lower abdomen or buttock), 30ml of adipose is aspirated through a cannula. That adipose is then processed in accordance with FDA guidelines including minimal manipulation (adipose only goes through a short, simple centrifugation to remove oils and leaves behind the fraction that contains mesenchymal stem cells).¹² Using of minimally manipulated, adipose derived stem cells has been shown safe for use as injection therapy for knee OA for 3 years.^{13,14}

Aim: To conduct a randomized trial comparing the clinical outcomes of PRP (standard intervention) versus Adipose-derived stem cells (investigational).

Hypothesis: Both interventions will result in significant improvement in patient-reported outcomes. We hypothesize that adipose-derived stem cells will provide superior outcomes.

Methods:

Participants / Outcome Measures / Sample size: Participants with symptomatic knee OA will be recruited from the sports medicine and orthopedics clinics, as well as advertising flyers within the clinic.

Inclusion / Exclusion Criteria

Inclusion criteria

Age 25-75 years

BMI < 40

Diagnosis of knee OA (primary and post-traumatic)

(Note: Participant may have OA in both knees, but only the most symptomatic knee will be treated as part of this trial so that patient reported outcomes are clearly defined for a single joint. The non-study knee may undergo all usual care prior to enrollment in the study, but no additional interventions can be performed during the course of the trial. If participant requires additional treatment, the participant will be unenrolled in the study).

Radiographic evidence of OA of the target knee (Kellgren-Lawrence grades 1-4)

Continued OA pain in the target knee despite at least 6 weeks of 1 of the following nonoperative treatments: activity modification, weight loss attempt, physical therapy, or NSAID / acetaminophen.

Knee Osteoarthritis Outcomes Score (KOOS)-Pain subscale 20-65

Working knowledge of English language (to be able to complete all outcome scores)

Ability to attend all follow-up appointments

Exclusion criteria

Isolated patellofemoral OA

3+ effusion of the target knee (stroke test grading system)

Significant (10 degree) valgus or varus deformities

Prior injection therapy:

Steroid injection in target knee in the last 3 months

Viscosupplementation in target knee in the last 6 months

PRP in the target knee in the last 1 year

Cellular treatments in index knee (bone marrow, amniotic suspensions etc) all time

Participation in any experimental device or drug study within 1 year before screening visit

Oral or IM steroids for last 3 months

Medical condition that may impact outcomes of procedure including:

anemia

thrombocytopenia

bleeding disorders

inflammatory disorders like rheumatoid arthritis, lupus

diabetes

any history of cancer (other than non-melanoma skin malignancies)

taking anticoagulants (aspirin, Plavix, eliquis, Xarelto, warfarin, lovenox)

Taking immunosuppressants, having a severe systemic infection

Previous cartilage repair procedure on the injured cartilage surface (ie, OATS, ACI, MFX)
Previous surgery at the target knee within the past 1 year
Any degree of cognitive impairment.
OA of either hip
Pregnancy, lactating, or intent to become pregnant during treatment period
Gout
History of infection or current infection at the affected joint
Smoking

Sample Size Calculation:

A total of 88 (44/group) participants will complete this two-treatment parallel-design study. The probability is 80 percent that the study will detect a treatment difference at a two-sided 0.05 significance level, if the true difference between treatments is 9 units. This is based on the assumption that the standard deviation of the response variable is 15.

We will enroll 110 (55/group) participants to ensure that 88 complete their 6 month visit assuming 80% follow up at the primary endpoint of the study.

Outcomes and Follow Up

Demographics collected

Age

Body mass index

Race

OA grade (as determined by KL stage on x-rays)

MRI severity (only if MRI within 1 year exists; no additional MRI will be ordered if participant does not have it) as determined by MOAKS score

The following outcomes will be collected at baseline, 1, 3, 6, and 12 months.

Adverse events

KOOS

VAS Pain (with ADLs)

Tegner

Additional baseline only measures: knee pain diagram and the pain catastrophizing scale

Additional 6 and 12 month only measures: failure (defined by failure to improve KOOS-P score, desire to seek additional treatment including injections or surgery) with failure at 6 months representing the primary outcome variable.

Follow-up plan:

All participants' first visit will be standard of care to provide a medical evaluation and assess best treatment plan for that participant, regardless of candidacy for this study. This evaluation includes x-rays of their knees as a standard part of the evaluation. This will be billed through insurance. If they meet criteria and choose to enroll, their procedure and all follow up visits will be covered by the research study funds. The schedule will be as follows (by group):

PRP:

- 1) Baseline (at time of enrollment during initial clinical evaluation, billed to insurance as standard evaluation, RedCap surveys administered in clinic)
- 2) Injection (REDCap surveys in clinic)
- 3) 1 month (REDCap surveys in clinic)
- 4) 3 months (REDCap surveys in clinic)
- 5) 6 months (REDCap surveys in clinic)
- 6) 12 months (REDCap surveys in clinic)

Adipose:

- 1) Baseline (at time of enrollment during initial clinical evaluation, billed to insurance as standard evaluation, RedCap surveys)
- 2) Injection
- 3) 2 weeks (in clinic wound-check, covered by research fund, no surveys)
- 4) 1 month (REDCap surveys in clinic)
- 5) 3 months (REDCap surveys in clinic)
- 6) 6 months (REDCap surveys in clinic)
- 7) 12 months (REDCap surveys in clinic)

Primary outcome: KOOS-Pain 6 months

Data will be housed in RedCap on a password protected, location secured medical center computer.

This study will utilize REDCap (Research Electronic Data Capture), a software toolset and workflow methodology for electronic collection and management of clinical and research data, to collect and store data. The Ohio State Center for Clinical and Translational Science (CCTS) Research Informatics Services will be used as a central location for data processing and management. REDCap provides a secure, web-based application that provides an intuitive data manipulation interface, custom reporting capabilities, audit trail functionality, real-time data monitoring/querying of participant records, and variations of data exporting/importing. REDCap is hosted by OSUWMC IT in the Ackerman Datacenter ([name])

REDCap instance is located on an internal OSUWMC network. Remote access to this network can be obtained over an encrypted VPN tunnel (AnyConnect). This VPN uses

Protocol: DTLS and Cipher: RSA_AES_128_SHA1. Background checks are performed on all staff that are on the network or obtaining VPN access.

Randomization

Participants will be randomized using randomization function available in RedCap.

Statistics

Continuous variables will be checked for normality and subsequently compared using either unpaired t-tests (for normally distributed data) or Mann-Whitney U test (for non-normally distributed data) at 6 months for the primary outcome. The variables will be analyzed again at 12 months..

After randomization, participants , medical staff and research team will note treatment arm allocation.

All participants will receive the following pre-procedural instructions

Avoid non-steroidal anti-inflammatories (NSAIDs) and aspirin for 14 days before the procedure.

No exercise the day before and the day of the procedure

Arrive to the procedure well-hydrated

Procedural Details

Platelet rich plasma

157mL of whole blood will be harvested via standard venipuncture from the antecubital fossa and mixed with 24mL ACD-A (manufacturer recommends 8mL ACD-A per 52mL of whole blood). 156ml of whole blood will be processed in the FDA Cleared Angel cPRP system at 2% hematocrit.

1ml of whole blood and the resultant PRP will be analyzed in the Sysmex XN-350 for complete analysis (platelet, leukocyte [total and differential], red blood cell counts). This data will be housed in the same RedCap system. The PRP left over after the Sysmex testing will be frozen in de-identified tubes in the -80C degree freezer on the 2nd floor of the Jameson Crane Sports Medicine Institute which is locked and only study staff have access to. At the conclusion of the study, this PRP will be thawed and sent for growth factor quantification (measuring transforming growth factor, platelet derived growth factor and interleukin-1). This analysis requires that all samples be completed in a single batch. For that reason, all samples will be kept in the freezer until the end of the study.

The remaining PRP (estimated 4-6mL) will be injected under sterile technique using ultrasound-guidance through a superolateral approach. For participant comfort, 2mL of 1% lidocaine can be administered using a 26-gauge needle (into soft tissues only). PRP will then be injected using a 25-gauge needle. A maximum of 6ml of PRP will be injected. Injection site will be cleaned and bandaged and participant will be dismissed with post-injection precautions and 1 month follow-up scheduled.

Adipose-derived stem cell

Adipose will be aspirated from the subcutaneous tissue of the buttock or abdomen (depending on best available specific to each participant). Once the area is prepared using standard sterile precautions, the aspiration site will be injected with 10ml 1% lidocaine with epinephrine. A small poke incision will be made with an 11-blade scalpel (to allow for aspiration cannula to be easily inserted). Then 120ml of Klein solution will be injected into the adipose tissue (facilitates ease of aspiration). Solution will sit for 15 minutes to allow for adequate anesthesia. Aspiration cannula will be inserted and carefully moved in a back and forth motion for 2 minutes to allow for ease of adipose aspiration. Then under continued sterile conditions, 30ml fat will be aspirated using 13G cannula. Aspiration site will be cleaned and bandaged. The aspirated fat will be immediately processed using the Lipogems system™ (Lipogems, Norcross, GA). This is a FDA cleared device that efficiently processes adipose to remove oil and leave mesenchymal stem cells for injection. Briefly, the 30ml of adipose is transferred to the device, saline is run through the device to remove oils and then approximately 5-7ml of adipose tissue is removed and ready for injection. This isolates the fraction of tissue that contains stem cells. The adipose derived cells are then injected in identical fashion to the PRP above (except an 18-gauge needle will be used for the injection due to higher viscosity).

0.5ml of adipose derived stem cells will be analyzed in the comparative orthopedics laboratory for total stem cell count and viability.

For both groups, if there is excess synovial fluid (an effusion), this will be removed (standard of care) prior to injecting the PRP or ADSC. This synovial fluid will be immediately analyzed for a complete blood count and then frozen in de-identified tubes in a locked -80C freezer on the second floor of the Jameson Crane Sports Medicine Institute. Only approved study staff will have access to this. At the conclusion of the study, all frozen samples will be analyzed for inflammatory proteins (IL-1, IL-8, TNF). This analysis requires that all samples be completed in a single batch. For that reason, all samples will be kept in the freezer until the end of the study.

Aftercare

Tylenol and ice are permissible for immediate pain control.

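### Unenrolling randomised participants who need additional treatment, with no later surveys planned, can bias the 6-month comparison if removal rates or score gaps differ by arm without cancelling

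*Combined protocol and SAP*

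**What the plan says.** The note under the inclusion criteria deals with participants who have OA in both knees. Only the more symptomatic knee is treated in the trial, "so that patient reported outcomes are clearly defined for a single joint". The other knee may have had usual care before enrolment, but "no additional interventions can be performed during the course of the trial". The next sentence is the rule at issue: "If participant requires additional treatment, the participant will be unenrolled in the study".

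Other sections bear on it:

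- **Sample Size Calculation:** "We will enroll 110 (55/group) participants to ensure that 88 complete their 6 month visit assuming 80% follow up". The expected loss is not split by cause.
- **Outcomes and Follow Up:** failure, assessed at 6 and 12 months, includes "desire to seek additional treatment including injections or surgery".
- **Follow-up plan:** surveys are scheduled at 1, 3, 6 and 12 months in both arms, and "their procedure and all follow up visits will be covered by the research study funds".
- **Statistics:** continuous variables are to be "compared using either unpaired t-tests (for normally distributed data) or Mann-Whitney U test" at 6 months and analysed again at 12. No analysis set or missing-data method is given. The section also says that participants, together with the "medical staff and research team will note treatment arm allocation", so the trial is open.
- **Aftercare:** Tylenol and ice are allowed, and over-the-counter NSAIDs during a flare.

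No section says whether an unenrolled participant continues the surveys.

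**The concern.** The rule removes people from a randomised comparison because of something that happens after randomisation. The groups compared at 6 months are then those still enrolled, not those randomised. What this costs depends on which knee the rule covers.

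- **Non-study knee (the likelier reading).** Treatment of the other knee does not make the study-knee KOOS-Pain score unusable, yet no later score is planned. The main cost is precision. The estimate also moves away from the all-randomised effect if those removed would have responded differently to the two treatments.
- **Study knee.** The need for treatment is then plausibly related to the outcome. A participant removed before month 6 leaves before failure is assessed, so the rule could remove people whom Outcomes and Follow Up would count as failures. Requiring treatment and wanting it are different events, so this is an overlap to reconcile, not a proven loss of failures. The rule cannot cover every study-knee treatment, because Aftercare permits some.

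Because allocation is known to everyone, the decision that a participant needs more treatment could differ between arms. That is plausible, but the documents do not show that it will happen. Removal after month 6 affects only the 12-month analysis.

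**Working it through.** **Inputs from Sample Size Calculation:** difference 9, SD 15, two-sided 0.05, power 80%, 44 completers per group, 110 enrolled, 80% follow-up. **Assumed here, because the documents give none:** removal rates, score gaps, and the gain from additional treatment. Differences are adipose minus PRP, with higher scores taken as better.

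**1. The plan's own figures.** The normal approximation gives n per group = 2 × (1.960 + 0.842)² × 15² / 9² = 43.6, so 44. Enrolment is 88 / 0.8 = 110. Both reproduce. Noncentral-t power at 44 per group is 79.5%, the baseline below.

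**2. When removal biases the comparison.** Let p be the proportion removed in an arm and g the retained mean minus the removed mean. The full mean is (1 − p) × retained + p × removed, so the retained mean exceeds it by p × g. Therefore

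observed difference = true difference + (p × g in adipose) − (p × g in PRP).

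There is no bias when the two products are equal. With a true difference of 9:

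- Equal rates, unequal gaps: 10% removed in both arms, gap 10 in adipose and 20 in PRP, gives 9 + 1.0 − 2.0 = 8.0.
- Unequal rates, random removal: both gaps are 0, so the result stays 9.
- Equal rates and equal gaps: the result stays 9.
- Equal 10% removal unrelated to arm, but no treatment effect among those removed: the retained difference is 9 / 0.9 = 10.0.
- One common score threshold (normal scores) removing the lowest 5, 10 or 20% of PRP: adipose loses about 1.2, 3.0 or 7.5%, and 9 becomes about 7.9, 7.1 or 6.0.

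**3. Size for a common gap g in both arms.** The difference becomes 9 − g × (PRP rate − adipose rate). Starting from 44 per group, with SD held at 15:

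| Removal, PRP v adipose | g = 10 | g = 20 |
|---|---|---|
| 10% v 5% (39.6 v 41.8 left) | 8.5, power 71% | 8.0, power 66% |
| 5% v 10% (41.8 v 39.6 left) | 9.5, power 81% | 10.0, power 84% |

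Equal removal of 5% leaves 9, with power 77%. With no true difference, a shift of 0.5 to 1.0 raises the false-positive rate from 5.0% to 5.3–6.0%.

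**4. Precision, if unenrolment is additional to the 20%.** Remaining per group = 44 × (1 − further loss). Enrolment needed to keep 88 = 88 / (0.8 × (1 − further loss)).

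| Further loss (assumed) | Left per group | Power at 9 | Enrolment needed |
|---|---|---|---|
| 5% | 41.8 | 77% | 115.8, so 116 |
| 10% | 39.6 | 75% | 122.2, so 123 |
| 15% | 37.4 | 73% | 129.4, so 130 |

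If the 20% already includes unenrolment, 44 per group remain and nothing is lost against the plan.

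**5. Keeping everyone instead.** Suppose 10% of PRP and 5% of adipose participants have additional treatment that adds h points. The difference is 9 − 0.05 × h: 8.5 for h = 10 and 8.0 for h = 20. With 44 per group kept, power is 75% and 70%. The shift matches the first row of step 3, without the lost scores.

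**The case against.** The strongest reply has five parts.

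- **The allowance may already cover the loss.** The 80% follow-up figure is not limited by cause, and a participant unenrolled before month 6 does not complete that visit. This stands: the power figures in steps 3 and 4 apply only if removal is additional. The allowance protects numbers, however, and cannot correct bias.
- **The outcome-related bias rests mainly on the less likely reading, and every rate and gap is assumed.** This stands as a limit on size. The figures are illustrations, not predictions. Holding SD at 15 is also unfavourable. If 15 is the SD before removal, the retained variance is 225 − p(1 − p)g². Averaged over the arms, the SD is then about 14.8 for g = 10 and 14.1 for g = 20, and the 71% and 66% become about 73% and 72%.
- **No section says scores are discarded.** This is correct. A reader might infer that the plan deletes scores already given. It does not say so, and the absence of later scores is inferred from silence. The consent pages are not in the text reviewed.
- **The plan has a reason for its rule, a clean single-joint outcome.** This is fair, and a sensitivity analysis can serve that aim.
- **The primary outcome is itself unclear.** Outcomes and Follow Up calls failure at 6 months primary, while the Follow-up plan section names KOOS-Pain at 6 months. The figures above apply to KOOS-Pain only.

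A reader might also infer that bias arises exactly when removal rates differ by arm. Step 2 shows otherwise: equal rates can bias, and unequal rates with random removal do not.

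**Conclusion.** The concern holds in this limited form. The plan removes randomised participants after a post-randomisation event, and it plans neither later surveys nor an all-randomised analysis. By inference, anyone unenrolled before month 6 contributes no 6-month study-knee score.

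Bias follows if rate times gap differs between arms, and it can go in either direction. With the assumed rates of 5% and 10% and a common gap of 10–20, a true 9 appears as 8.0–8.5 or 9.5–10.0. A common score threshold could shift it further. If there is no treatment effect and the removal process is identical in both arms, the only cost is precision.

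The documents do not support saying that the trial will be underpowered, that removal will differ by arm, or that failures will certainly be dropped. The power loss is nil if the 20% covers unenrolment, and otherwise 79.5% falls to 77–73% for an assumed 5–15% further loss. Open allocation makes differential removal plausible without proving it. The point should be fixed, with medium confidence, chiefly because the remedy is cheap.

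**What to change.** 1. State which knee the rule covers. Reconcile it with the failure definition in Outcomes and Follow Up and with the treatments permitted in Aftercare. This need not change which treatments are allowed.
2. Replace removal from data collection with continued scheduled KOOS surveys for all consenting randomised participants. Record any additional treatment, the knee and the date.
3. Make the primary 6-month comparison by assigned arm, using every available score whatever additional treatment was given. The planned t-test or Mann-Whitney test can stay. Report the analysis excluding participants with additional treatment as a sensitivity analysis.
4. Say whether the 20% loss allowance includes unenrolment.

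The cost is mainly protocol wording, since the visits and surveys are already scheduled and funded. The downside is that the estimate becomes a treatment-policy effect and may be smaller (8.5–8.0 in step 5). The gain is a comparison of the groups as randomised without avoidable loss of scores, not a larger difference. Ordinary dropout would remain and needs its own missing-data plan, a separate matter.

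### KL grade spans 1 to 4 at entry and is recorded before treatment, but the planned 6-month comparison does not use it, which gives up a modest gain in precision that needs no new data

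*Combined protocol and SAP*

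**What the plan says.** Structural severity is left wide at entry. The inclusion criteria require "Radiographic evidence of OA of the target knee (Kellgren-Lawrence grades 1-4". Symptoms are bounded separately, by "Knee Osteoarthritis Outcomes Score (KOOS)-Pain subscale 20-65", which limits the pain score but not the radiographic grade.

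Grade is collected: the list under Demographics collected includes "OA grade (as determined by KL stage on x-rays". The Follow-up plan makes knee x-rays part of the first visit, and grade is itself an entry criterion, so it is known before allocation.

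Allocation is described in one sentence: "Participants will be randomized using randomization function available in RedCap". No strata and no blocks are named. The Statistics section gives a single analysis rule, a t-test or a Mann-Whitney U test according to a normality check, with no covariate.

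The Sample Size Calculation states: "A total of 88 (44/group) participants will complete this two-treatment parallel-design study". It is set to "detect a treatment difference at a two-sided 0.05 significance level, if the true difference between treatments is 9 units", and adds: "This is based on the assumption that the standard deviation of the response variable is 15". Enrolment follows from expected loss: "We will enroll 110 (55/group) participants to ensure that 88 complete their 6 month visit assuming 80% follow up".

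**The concern.** Knees from the mildest to the most severe radiographic grade enter a trial with 44 completers per arm. If grade predicts pain at 6 months, two things follow from leaving it out of the analysis. Variation that the model could explain stays in the error term, so the standard error is larger than it need be. And if the arms end up with a different mix of grades, readers will ask how much of the observed difference reflects that mix, with no planned analysis to answer them.

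The second matters more because participants, clinical staff and the research team all know the arm after randomisation. An adjustment for grade chosen after an imbalance is seen would be open to challenge. One named in advance would not. There is also little spare power, since the design sits at its 80% target.

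**Working it through.** **Inputs from the document** (Sample Size Calculation): difference 9, SD 15, two-sided 0.05, 80% power, 44 completers per arm, 80% follow-up.

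**Inputs assumed, because the document gives none:** half the knees are grade 3-4 (p = 0.5); grade 3-4 knees score g = 5 to 10 points lower on KOOS-Pain at 6 months, with g = 15 shown as a stress case; SD 15 describes the 6-month score in the enrolled mix of grades.

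**1. The plan's own figures.**
- n per arm = 2 × (1.96 + 0.842)² × 15² / 9² = 43.6, rounded up to 44.
- SE of the difference = 15 × √(2/44) = 3.20 units.
- Power = Φ(9/3.20 − 1.96) = 80.4% (79.5% by the noncentral t).
- Enrolment = 88 / 0.80 = 110.

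All stated figures reproduce.

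**2. Chance imbalance in grade, if allocation takes no account of it.** SD of the between-arm difference in the share of grade 3-4 knees = √(2 × 0.5 × 0.5 / 44) = 10.7 percentage points; 95% range ±1.96 × 10.7 = ±20.9 points. The resulting shift in the treatment difference is the imbalance multiplied by g.

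**3. Gain from adjustment.** Share of variance explained R² = 0.25 × g² / 225. Adjusted SE = 3.20 × √(1 − R²). Power = Φ(9/adjusted SE − 1.96).

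| g | R² | Adjusted SE | Cut in SE | Power at 44 per arm | Shift at 1 SD of imbalance | Shift at the 95% limit |
|---|---|---|---|---|---|---|
| 0 | 0 | 3.20 | 0% | 80.4% | 0 | 0 |
| 5 | 0.03 | 3.15 | 1% | 81.4% | 0.5 (6% of 9) | 1.0 (12% of 9) |
| 10 | 0.11 | 3.02 | 6% | 84.7% | 1.1 (12%) | 2.1 (23%) |
| 15 | 0.25 | 2.77 | 13% | 90.1% | 1.6 (18%) | 3.1 (35%) |

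With 30% of knees at grade 3-4 instead of half, power is 81.3% (g = 5) or 84.0% (g = 10), and the 95% limits of the shift are 1.0 and 1.9 units.

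**4. Check by simulation** (20,000 trials per scenario, total SD 15). At g = 10, the unadjusted t-test had type I error 4.8% and power 79.5%; the model with grade had 4.8% and 83.4%. At g = 15, type I error was 4.7% unadjusted and 5.0% adjusted, and power was 79.5% and 89.4%. The simulated gain at g = 10 is thus slightly below the formula's.

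**5. The unlucky trial.** Given an imbalance at its 95% limit, the conditional type I error of the unadjusted test is about 6% (g = 5) or 9% (g = 10). Averaged over all allocations it stays near 5%, as step 4 shows.

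**The case against.** The strongest reply is that randomisation already deals with this. The planned SE of 3.2 units implies an ordinary 95% sampling range of about ±6.3 units (1.96 × 3.20). If SD 15 describes the enrolled mix, that range already contains the ±1.0 to ±2.1 that grade could contribute. The test is valid without adjustment, and at the lower assumed gap the gain is close to nothing. All of this stands, and it limits the point to precision and interpretation.

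Broad entry is also a legitimate pragmatic choice. The exclusions for 10-degree deformity, 3+ effusion and isolated patellofemoral disease narrow the population in other ways. Nothing here argues for narrower entry.

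Three stronger readings are tempting, and the documents do not support them:

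- *That allocation is unstratified.* The protocol is silent. The REDCap function may or may not have been set up with strata. The supportable statement is that none is specified. If strata were used, the planned test ignores them, and its standard error is too large when grade predicts outcome. The analysis change is right in either case.
- *That imbalance could move the result by a sizeable part of the 9-unit target.* The 12% to 23% is reached only at the 95% limit of imbalance, under an assumed mix and gap. At 1 SD it is 6% to 12%. At g = 10, a shift of 3 units or more has a probability of about 0.5%.
- *That the treatment effect differs by grade.* It may, but the figures above concern grade as a predictor of outcome. A main-effect term for grade neither estimates nor resolves a treatment-by-grade difference.

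**Conclusion.** The point holds as an improvement that costs no new data, not as an error that threatens validity. A baseline severity measure that plausibly predicts outcome is collected and then left out of the only planned comparison. There is no bias and no inflation of overall type I error. What is lost is a 1% to 6% reduction in the standard error, and a prepared answer if the arms differ in grade.

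That size rests on a grade mix and a grade effect that are assumed. If grade hardly predicts 6-month KOOS-Pain, the gain is negligible; at a 15-point gap it would be substantial. It may also shrink once baseline KOOS-Pain is in the model, since the two may share information about outcome.

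The argument applies to KOOS-Pain at 6 months, which the Follow-up plan names as primary. The Outcomes and Follow Up section instead gives that role to failure at 6 months. That conflict is a separate matter and must be reconciled; the 9-unit and SD 15 inputs fit only a continuous score.

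**What to change.** Replace the t-test/Mann-Whitney rule for 6-month KOOS-Pain with a prespecified linear model (ANCOVA) containing treatment, KL grade (1-2 versus 3-4, as read before randomisation) and baseline KOOS-Pain. A covariate cannot simply be added to the present rule, because neither test takes one. Keep the unadjusted comparison as a sensitivity analysis.

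State in the Randomization section whether the REDCap allocation is stratified and blocked. If it is stratified, include the stratum in the model.

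Changing the allocation table during enrolment is optional and secondary. With 20% expected loss, stratifying the 110 enrolled would not guarantee balance among the 88 completers, and grade would have to be entered before each allocation. If enrolment is complete, only the analysis change applies.

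The cost is a short amendment to the Statistics section, made before outcome data are compared by arm. Grade and baseline KOOS-Pain are already collected.

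### Binary failure at 6 months and KOOS-Pain at 6 months are both named primary; the 80% power and the planned tests fit only a continuous outcome, and failure is not fully defined.

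*Combined protocol and SAP*

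**What the plan says.** All references are to the combined protocol and SAP.

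- **Outcomes and Follow Up** introduces, for 6 and 12 months only, "failure (defined by failure to improve KOOS-P score, desire to seek additional treatment including injections or surgery", and continues "with failure at 6 months representing the primary outcome variable".
- **Follow-up plan**, after the visit schedules, states: "Primary outcome: KOOS-Pain 6 months".
- **Sample Size Calculation**: "A total of 88 (44/group) participants will complete this two-treatment parallel-design study". The power is 80% at two-sided 0.05 "if the true difference between treatments is 9 units", assuming that "the standard deviation of the response variable is 15". The response variable is not named. Enrolment is 110, to allow for 80% follow-up at 6 months.
- **Statistics** plans unpaired t-tests or Mann-Whitney tests for continuous variables at 6 months for the primary outcome. It gives no method for a binary outcome, and states that participants, medical staff and the research team will note the allocation.
- **Inclusion criteria**, in the note on bilateral disease: "If participant requires additional treatment, the participant will be unenrolled in the study". This follows directly on a sentence about the non-study knee.

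**The concern.** Two different variables carry the primary label, and the plan's power and tests match only one of them. If failure is taken as primary, the trial has no sample size justification and no stated analysis for it.

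Nor can failure be computed reproducibly. A comma separates its two parts; the only *or* joins injections and surgery. A participant might therefore need to meet both parts or just one. No size of improvement is given, so on a literal reading the KOOS part counts any rise as improvement. How desire for treatment is to be measured is not stated. These choices could be made after the data are seen.

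The unenrolment sentence adds a further risk. If it is also applied to the target knee, people who need more treatment leave before month 6, although they are the people a failure endpoint is meant to count. With allocation known, treatment seeking may differ between arms for reasons other than efficacy, and their removal could bias the comparison.

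**Working it through.** **1. The plan's own figure.** Inputs from Sample Size Calculation: difference 9, SD 15, two-sided 0.05, 80% power.

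n per group = 2 × (1.960 + 0.842)² × 15² / 9² = 43.6, so 44. Power at 44 = Φ(9 / (15 × √(2/44)) − 1.960) = 80.4% (79.5% with the t distribution). Enrolment: 88 / 0.80 = 110. The figures reproduce, as a comparison of two means.

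**2. The KOOS part of failure on the same inputs.** From the plan: difference 9 and 44 per group. Assumed: SD 15 applies to change scores, change is normal, and PRP gains 10, 15 or 20 points on average (adipose 9 more). Failure means change ≤ 0.

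- Failure probability = Φ(−mean gain / 15).
- Power = Φ((|p₁ − p₂| − 1.960 × se₀) / se₁), where se₀ = √(2p̄(1 − p̄)/44) and se₁ = √((p₁(1 − p₁) + p₂(1 − p₂))/44).
- Example, PRP gain 10: p₁ = Φ(−0.667) = 0.252; p₂ = Φ(−1.267) = 0.103; se₀ = 0.0815; se₁ = 0.0799; power = Φ((0.150 − 0.160)/0.0799) = 45%.

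| PRP mean gain | Failure, PRP v adipose | Power by formula | Power, exact enumeration of the pooled z-test | Per arm for 80% |
|---|---|---|---|---|
| 10 | 25.2% v 10.3% | 45% | 47% | 101 |
| 15 | 15.9% v 5.5% | 35% | 38% | 138 |
| 20 | 9.1% v 2.7% | 25% | 26% | 208 |

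Sensitivity: Fisher's exact test gives 35%, 23% and 8%. With a change SD of 20 the formula gives 32%, 28% and 24%. With a PRP gain of only 5 and SD 15 it gives about 53%.

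**3. The and/or rule.** Central case, all assumed: PRP gain 15, SD 15, 30% of PRP participants wanting more treatment, latent correlation 0.5 between the two parts.

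| Effect of arm on desire | Rule | Failure, PRP v adipose | Power at 44 per arm |
|---|---|---|---|
| Shifted by 9/15 = 0.6 SD | and | 9.6% v 2.5% | 29% |
| Shifted by 0.6 SD | or | 36.3% v 16.1% | 58% |
| None | and | 9.6% v 3.9% | 18% |
| None | or | 36.3% v 31.6% | 7% |

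Over PRP gains of 10-20, desire of 20-40% and correlations of 0-0.8, PRP failure runs from 2% to 22% under *and* and from 22% to 55% under *or*. Power runs from 8% to 43% and from 3% to 74% respectively. No setting reaches 80%.

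**4. The unenrolment sentence.** Its own words are not limited to one knee, but its position ties it to the non-study knee. Both readings are open. Only if it reaches the target knee does it conflict with the failure endpoint.

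**The case against.** The strongest reply is that KOOS-Pain is the real primary outcome. It has its own line, and the sample size and tests agree with it, so low power for failure would be a minor matter. That is persuasive about intent and supports the fix, but the plan still gives failure the primary label, so the contradiction stands.

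Several stronger readings are tempting and are not supported:

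- *The plan sets a zero cut-off, so any rise is a success.* It sets no cut-off; zero is the literal reading of the KOOS part. Under *or*, a participant who improves but wants more treatment still fails.
- *The 9 units is the plan's improvement threshold.* It is a between-group mean difference, not a criterion for one person's change.
- *The plan removes treated participants before they can be counted.* The sentence sits in a note on the other knee, and treatment of that knee is not failure of the study knee.
- *The 25-47% is the power of the failure endpoint.* It covers the KOOS component alone, and rests on assumed gains and on using SD 15 for change.

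It is also fair to say that settling the definition does not rescue power. Under *or* with a zero cut-off, the same grid gives 43-74% if desire shifts by 0.6 SD between arms, but 3-22% if it does not differ. Desire is also a subjective item in a trial where allocation is known. Both are reasons to keep failure out of the primary position.

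**Conclusion.** The concern holds in this form. Two primary outcomes are named; the 80% power and the planned tests belong to a continuous one, and failure lacks a combining rule, an expected rate and a binary test. The contradiction and the omissions rest on the text alone. The size rests on assumptions, because the documents give no failure rate: the KOOS component at a zero cut-off has about 25-47% power for assumed PRP gains of 10-20 with change SD 15, and the and/or choice moves the central PRP rate from 9.6% to 36.3%. The loss of failures through unenrolment is conditional on that rule being applied to the target knee.

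**What to change.** 1. Reconcile the two statements: make KOOS-Pain at 6 months the single primary outcome, attach the 80% power statement to it by name, and list failure as secondary.
2. Define failure as **either** no improvement in KOOS-Pain from enrolment **or** receipt of, or stated desire for, a further injection or surgery on the target knee. Compare the arms with a named test for proportions and report each component separately. Fix any non-zero improvement threshold before analysis, show it as a sensitivity analysis, and do not present it as the plan's 9 units.
3. Reconcile the unenrolment sentence with the failure endpoint and state which knee it concerns. Record the reason for leaving and the knee treated. In the analysis of all randomised participants, score those who left for additional target-knee treatment as failures, and do not count treatment of the other knee as failure. State a rule for those missing for other reasons, since 20% loss is expected.

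The cost is mostly wording. Receipt of further treatment, the reason for leaving and the knee concerned are not among the listed outcomes, so a small amount of data capture is added. The threshold in the sensitivity analysis remains a convention.
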